### **3.2. Randomization and Blinding**

This study will be conducted in a double-blind, placebo-controlled manner. Enrolled patients who meet all eligibility requirements will be randomized in a 1:1 ratio to 1 of 2 treatment groups: placebo or OCA based on a predefined randomization code (generated by Sponsor or designee) using an interactive web response system (IWRS), which the Sponsor intends will serve as a computer-based patient registration system at Screening and Day 1.

Randomization will be stratified by CP class (CP-B or CP-C). Baseline MELD scores will be monitored on an ongoing basis to ensure adequate distribution of MELD scores. The IWRS will serve as the IP inventory and management system and may be integrated with the study database.

The Investigator or designee will be required to register the patient in the IWRS and may be prompted to provide patient data necessary to properly randomize and allocate the patient to treatment. A randomization number will be assigned and IP (placebo or OCA) dispensing information will be provided (eg, bottle numbers allocated) while maintaining the study blind.

The sponsors, patients, investigators, and study site staff will be blinded to the patient's treatment allocation during the patient's participation in the double-blind phase of the study.

Treatment assignment for individual patients will be made available to the Investigator for medical emergency use only (such as unblinding which is necessary in order to treat a serious adverse event through the IWRS system). When possible, the Medical Monitor should be consulted in the event that a medical emergency necessitates unblinding (ie, in situations where knowledge of the blinded treatment assignment is necessary for further medical management of the patient). If it is not reasonable to inform the Medical Monitor in advance of the unblinding, the Investigator must promptly document in the patient's record the rationale for unblinding and should subsequently contact the Medical Monitor to explain any premature unblinding of treatment assignment. Procedures for unblinding a patient's treatment will be provided separately to the Investigator. Similarly, if the Medical Monitor breaks the blind for an individual patient for the purpose of evaluating an emergent safety issue, the Medical Monitor will document within study documentation the rationale, circumstances, and the person or persons being informed about the unblinding.

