### **3.3. Sample Size Determination**

To reasonably characterize the PK of OCA in patients with hepatic impairment, a simulation-based approach estimated a requirement of approximately 20 patients in the OCA treatment group assuming a 15% discontinuation rate. A total of 30 patients is adequate with 10 patients on placebo to be included as a comparator and 20 patients on OCA. An additional 20 patients will be enrolled to support safety and efficacy evaluations. Therefore, approximately 50 patients (including at least 20% of patients with CP-C) will be randomized in a 1:1 ratio to 1 of 2 treatment groups: placebo and OCA.

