## 9. EFFICACY ANALYSES

The efficacy endpoints of the study are defined below. Additionally, the planned analyses for these endpoints are described.

The efficacy analyses are additional endpoint in this study and will be performed on the ITT Population, as defined in [Section 4.2](#). Summary statistics will be tabulated for baseline, change and percent change from baseline to each scheduled visit of DB phase, Week 48 (end of DB phase), and each scheduled visit of DB extension (DBext) phase. An analysis of covariance (ANCOVA) model and Wilcoxon Rank Sum Test will be applied to the change and percent change from baseline to Week 48 and each scheduled visit of DB phase of efficacy parameters. All CIs for point estimates provided will be conducted using the two-sided 95% confidence intervals.

All efficacy data will be provided in listings by subject and visit.

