### 9.1. MELD Score

MELD score is derived from the patient's serum total bilirubin, serum creatinine, and INR, as appropriate, to predict survival ([Kamath 2007](#)). MELD score will be calculated and reported for visits where these parameters are measured as described in the protocol. An increasing MELD score is associated with increased severity of hepatic dysfunction and increased 3-month mortality risk.

- Summary statistics of MELD score including baseline values, change from baseline, and Percentage change from baseline values will be presented by treatment group and by each scheduled post-baseline visit.
- Analysis of change from baseline in MELD score will be analyzed using the Wilcoxon Rank Sum Test. The tabulation will include median, interquartile range for each treatment group, median differences and 95% CI of the median differences between treatment groups using the Hodges-Lehmann estimate. If the median differences between treatments are not symmetrical around the median, the Sign Test may be used.
- MELD score will be presented in shift tables showing the shift from baseline to each scheduled post-baseline visit by the count and percentage of patients within each shift classification (<10, 10 to <12, 12 to <13, 13 to <14, 14 to <15, and  $\geq 15$ ).

The MELD Score analyses will be repeated for MELD-Na

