**Table 2: Child-Pugh Scoring System**

Factor	Units	Points		
		1	2	3
Serum bilirubin	µmol/L	<34	34-50	>50
	mg/dL	<2.0	2.0-3.0	>3.0
Serum albumin	g/L	>35	28-35	<28
	g/dL	>3.5	2.8-3.5	<2.8
Prothrombin time	Seconds prolonged	0-3	4-6	>6
	INR	<1.7	1.7-2.3	>2.3
Ascites		None	Mild	Moderate-Severe
Hepatic encephalopathy a		0	Grade 1 or 2	Grade 3 or 4

a Grade 0: normal consciousness, personality, neurological examination, electroencephalogram  
 Grade 1: restless, sleep disturbed, irritable/agitated, tremor, impaired handwriting, 5 cps waves  
 Grade 2: lethargic, time-disoriented, inappropriate, asterixis, ataxia, slow triphasic waves  
 Grade 3: somnolent, stuporous, place-disoriented, hyperactive reflexes, rigidity, slower waves  
 Grade 4: unrousable coma, no personality/behavior, decerebrate, slow 2-3 cps delta activity  
 (Pugh 1973, Lucey 1997), Vilstrup 2014

- Baseline CP score is calculated based on components measured at Screening visit.
- Summary statistics of CP score including baseline values, change from baseline, and percentage change from baseline values will be presented by treatment group and by each scheduled post-baseline visit.
- Analysis of change from baseline in CP score will be analyzed using the Wilcoxon Rank Sum Test. The median differences and 95% CI of the median differences between treatment groups will be constructed using the Hodges-Lehmann estimate. If the median differences between treatments are not symmetrical around the median, the Sign Test may be used.
- CP class (A, B, and C) will be presented in a shift table showing the shift from baseline to each scheduled post-baseline visit by the count and percentage of patients within each shift classification (A, B, and C).
- Components of CP score categories as listed in Table 2 will be summarized by the count and percentage of patients within each category at baseline and each scheduled post-baseline visit.

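### The Sign Test fallback for MELD and Child-Pugh does not fit two unpaired arms, and its symmetry trigger belongs to a different test

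*SAP*

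**What the plan says.** SAP Section 9.1: "Analysis of change from baseline in MELD score will be analyzed using the Wilcoxon Rank Sum Test". The tabulation gives medians and interquartile ranges by arm, and the "95% CI of the median differences between treatment groups using the Hodges-Lehmann estimate". The fallback follows: "If the median differences between treatments are not symmetrical around the median, the Sign Test may be used". The section closes by repeating the MELD analyses for MELD-Na.

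SAP Section 9.2, in the list under Table 2: "Analysis of change from baseline in CP score will be analyzed using the Wilcoxon Rank Sum Test", with the same Hodges-Lehmann estimate and the same fallback sentence.

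SAP Section 3.2 describes a parallel design: patients are "randomized in a 1:1 ratio to 1 of 2 treatment groups: placebo or OCA". Stratification is by Child-Pugh class. No matching or pairing of patients appears anywhere.

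The opening of SAP Section 9 plans between-arm testing for Week 48 and the scheduled double-blind-phase visits. Extension visits get summary statistics only.

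**The concern.** The sentence has three faults.

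1. **The test does not fit the design.** A Sign Test counts positive and negative signs in one sample or in paired differences. Two independent arms supply no pairs.
2. **The trigger is misplaced.** Symmetry about the median is what the one-sample or paired signed-rank test needs, and the Sign Test is the usual retreat when it fails. The rank-sum test has no such requirement.
3. **The switch is open.** The wording is permissive. It gives no measure of asymmetry, no threshold, no statement of when or by whom it is judged, and no implementation.

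At stake is the p-value for two secondary endpoints and MELD-Na, in a trial of about 50 patients where hepatic function will be read closely. Section 1 has deviations from the SAP documented in the study report. A switch made under this sentence would count as planned and so would not be flagged as a deviation.

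**Working it through.** **Plan's own figure.** None exists to reproduce: the SAP gives no power, alpha or sample size for this comparison. The check is therefore on the logic, supported by simulation.

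**Inputs from the SAP.** "approximately 50 patients (including at least 20% of patients with CP-C) will be randomized in a 1:1 ratio" (Section 3.3), so 50 / 2 = 25 per arm. The same section has "approximately 20 patients in the OCA treatment group assuming a 15% discontinuation rate". Applying that 15% to both arms is my assumption: 25 × 0.85 = 21.25, about 21 per arm. Intervals are two-sided 95% (Section 9), so tests were run two-sided at 0.05.

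**Assumed, not in the SAP.** Changes are (a) normal, SD 2; (b) skewed: exponential, scale 2, centred at median 0; (c) skewed and rounded to integers: round(exponential with scale 2, minus 1); (d) exponential, scale 2, uncentred, so that every patient in both arms worsens. The treatment shift is 0 or 1.5 points. There were 4,000 runs per scenario, so the Monte Carlo standard error near 0.05 is √(0.05 × 0.95 / 4000) = 0.003.

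**Rejection rates**

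| Scenario | n per arm | Shift | Rank-sum | Sign, within OCA arm | Sign, arbitrary OCA-placebo pairs |
|---|---|---|---|---|---|
| (a) normal | 25 | 0 | 0.051 | 0.037 | 0.046 |
| (b) skewed | 25 | 0 | 0.048 | 0.046 | 0.040 |
| (c) skewed, ties | 25 | 0 | 0.050 | 0.252 | 0.028 |
| (d) both arms worsen | 25 | 0 | 0.050 | 1.000 | 0.044 |
| (b) skewed | 21 | 0 | 0.050 | 0.025 | 0.027 |
| (a) normal | 25 | 1.5 | 0.717 | 0.816 | 0.529 |
| (b) skewed | 25 | 1.5 | 0.909 | 1.000 | 0.772 |

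**Step 1, the trigger.** Rank-sum type I error lies between 0.048 and 0.051 with symmetric, skewed and tied data. Skewness does not disturb it. The one-sample signed-rank test on scenario (b), true median 0, rejects in 12% of runs at n = 25 and 21% at n = 50, while the Sign Test stays at 4.3% and 3.5%. The SAP sentence suits that setting, which is not this trial's.

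**Step 2, the fallback read as a within-arm test.** It tests change against zero and leaves placebo out. In (d) it rejects every time with no treatment difference. That scenario is extreme by construction, since all 25 signs are positive. Scenario (c) is milder: P(change < 0) = 1 − e^(−0.25) = 0.221, P(change = 0) = e^(−0.25) − e^(−0.75) = 0.306, P(change > 0) = e^(−0.75) = 0.472. There the within-arm test still rejects in 25% of runs with identical arms. It also discards the 31% of patients with zero change.

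**Step 3, the fallback read as pairing OCA with placebo patients.** Random pairing holds its size, but the answer depends on the draw. In one simulated data set (skewed, shift 1.2, rank-sum p = 0.006), 5,000 re-pairings gave Sign Test p-values from 0.0002 to 0.69, with 69% below 0.05. Power also falls: 0.77 against 0.91 for the rank-sum test in scenario (b).

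**Step 4, internal comparison.** Section 9.4 uses the rank-sum test for bile acids, C4 and FGF-19 with no Sign Test fallback, so the SAP does not treat symmetry as a general condition of that test. Section 9.3 shows how a fallback can be fixed: it orders the covariance structures to be tried and ties each step to non-convergence.

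**The case against.** The strongest defence is that little depends on the sentence. Section 2.2 states that no formal hypothesis is tested. The primary objectives are PK and safety, and MELD and Child-Pugh are secondary. The fallback is optional, and the medians and Hodges-Lehmann intervals are planned whether or not it is used. All of this stands, and it limits the size of the point.

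Three stronger readings are tempting, and the SAP does not support them.

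- **That the trigger would often be met because MELD and Child-Pugh changes are discrete and skewed.** The trigger concerns differences between treatments. If OCA changes are distributed as placebo changes plus a constant δ, then (OCA − placebo − δ) is the difference of two independent draws from one distribution, which is symmetric about 0 however skewed that distribution is. The simulated mean skewness of the pairwise differences was 0.01. On that reading the trigger needs arms of unequal shape, and the SAP gives no data on how often that would happen.
- **That within-arm tests replace the treatment comparison.** The sentence speaks of differences between treatments, never mentions change against zero, and withdraws nothing. The within-arm version is one of two ways it might be carried out.
- **That every post-baseline visit is affected.** Section 9 confines between-arm testing to the double-blind phase.

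It can also be argued that the Sign Test is a loose name for a two-sample median test. The SAP does not say so. Uncorrected Mood's test had type I error of 0.06 to 0.10 in these simulations and less power than the rank-sum test in the scenarios run.

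Unequal shapes would make the Hodges-Lehmann estimate harder to read as a shift, but a Sign Test does not cure that.

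**Conclusion.** The point holds as a test-specification error, stated in Sections 9.1 and 9.2 and carried to MELD-Na. The named fallback is not a valid comparison of two unpaired arms, its trigger is not an assumption of the planned test, and the choice is left open to the data. It reaches Week 48 and the other double-blind-phase visits.

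Its size is small: optional p-values on secondary endpoints with no formal hypothesis, and effect estimates that are reported regardless. It should be corrected, but no primary conclusion rests on it. The design argument needs no distributional assumption. The simulated rates rest on the assumed distributions and shifts and illustrate the mechanism; they do not predict what this trial would show.

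**What to change.** Delete the Sign Test sentence from SAP Sections 9.1 and 9.2. Keep the rank-sum test, the Hodges-Lehmann estimate and its 95% CI whatever the symmetry. MELD-Na then follows without further edits.

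If the sponsor wants a fallback, it should name a valid two-sample method and fix the rule for using it before unblinding. That is optional; deletion alone is enough.

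The cost is two deleted sentences, with no change to data collection, sample size or the planned tabulations.

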### 9.2. Child-Pugh (CP) Score

CP Score (Pugh 1973, Lucey 1997) is calculated and reported within the EDC system based on data entered into the eCRF by adding the scores from the 5 factors outlined in [Table 2](#) and can range from 5-15. A total score of 5-6 is considered Grade A (mild, well-compensated disease); 7-9 is Grade B (moderate, significant functional compromise); and 10 and above is Grade C (severe, decompensated disease). Calculation of the CP score includes Investigator assessments of ascites and hepatic encephalopathy, which may be assessed during the adverse event review at

the scheduled visits, as well as total bilirubin, serum albumin, and prothrombin time, which will populate from the central laboratory.

**Table 2: Child-Pugh Scoring System**

Factor	Units	Points		
		1	2	3
Serum bilirubin	µmol/L	<34	34-50	>50
	mg/dL	<2.0	2.0-3.0	>3.0
Serum albumin	g/L	>35	28-35	<28
	g/dL	>3.5	2.8-3.5	<2.8
Prothrombin time	Seconds prolonged	0-3	4-6	>6
	INR	<1.7	1.7-2.3	>2.3
Ascites		None	Mild	Moderate-Severe
Hepatic encephalopathy a		0	Grade 1 or 2	Grade 3 or 4

a Grade 0: normal consciousness, personality, neurological examination, electroencephalogram  
 Grade 1: restless, sleep disturbed, irritable/agitated, tremor, impaired handwriting, 5 cps waves  
 Grade 2: lethargic, time-disoriented, inappropriate, asterixis, ataxia, slow triphasic waves  
 Grade 3: somnolent, stuporous, place-disoriented, hyperactive reflexes, rigidity, slower waves  
 Grade 4: unrousable coma, no personality/behavior, decerebrate, slow 2-3 cps delta activity  
 (Pugh 1973, Lucey 1997), Vilstrup 2014

- Baseline CP score is calculated based on components measured at Screening visit.
- Summary statistics of CP score including baseline values, change from baseline, and percentage change from baseline values will be presented by treatment group and by each scheduled post-baseline visit.
- Analysis of change from baseline in CP score will be analyzed using the Wilcoxon Rank Sum Test. The median differences and 95% CI of the median differences between treatment groups will be constructed using the Hodges-Lehmann estimate. If the median differences between treatments are not symmetrical around the median, the Sign Test may be used.
- CP class (A, B, and C) will be presented in a shift table showing the shift from baseline to each scheduled post-baseline visit by the count and percentage of patients within each shift classification (A, B, and C).
- Components of CP score categories as listed in Table 2 will be summarized by the count and percentage of patients within each category at baseline and each scheduled post-baseline visit.

### 9.3. Liver Biochemistry and Hepatobiliary Damage

Liver biochemistry includes total and direct bilirubin, ALP, ALT, AST, and GGT, INR, creatinine, albumin, and platelets.

- Summary statistics of liver biochemistry including baseline values, change from baseline, and percentage change from baseline values will be provided by treatment group and by each scheduled post-baseline visit.
- Change from baseline will be analyzed by using an ANCOVA model with change from baseline as the dependent variable, treatment group and randomization stratification factor as fixed effects and the baseline value as a covariate.
- Percent change from baseline will be analyzed by using an ANCOVA model with percent change from baseline as the dependent variable, treatment group and randomization stratification factor as fixed effects and the baseline value as a covariate.
- As a sensitivity analysis, change from baseline and percent change from baseline of liver biochemistry parameters will be analyzed by using a restricted maximum likelihood (REML) based MMRM. Treatment group, time, treatment group by time interaction, and randomization stratification factor will be included as fixed effects and parameter baseline values will be included as a covariate in the model, where time includes all post baseline visits of DB phase.
- An unstructured covariance structure will be used to model the within-participant errors. If there is a convergence issue with the unstructured covariance model, Toeplitz, Autoregressive (1) (AR (1)) covariance structure will be used, following this sequence until convergence is achieved. If the model still does not converge with AR (1) structure, no results will be reported. When the covariance structure is not unstructured, the sandwich estimator for the variance-covariance matrix will be derived, using the EMPIRICAL option in the PROC MIXED statement in SAS. The p-value will be interpreted at 0.05 level of significance.
- The tabulation of ANCOVA model and MMRM model will include estimates of least-square (LS) means, SEs, and 2-sided 95% CIs for each treatment group. Estimates of the mean difference, SE of the difference, 2-sided 95% CI of the difference between treatment groups, and p-value will also be presented.

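### The MMRM fallback uses the classical sandwich variance with about 50 subjects and no small-sample correction, so on average its standard errors are modestly too small

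*SAP*

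**What the plan says.** SAP Section 9.3 analyses ten liver biochemistry parameters by ANCOVA. As a sensitivity analysis it adds a REML-based MMRM for change and percent change. For the mean model it states: "Treatment group, time, treatment group by time interaction, and randomization stratification factor will be included as fixed effects", with the baseline value as covariate and all post-baseline double-blind visits in the time factor.

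The covariance starts as unstructured. The fallback reads: "If there is a convergence issue with the unstructured covariance model, Toeplitz, Autoregressive (1) (AR (1)) covariance structure will be used". For any structure other than unstructured, the variance comes from a sandwich estimator, obtained "using the EMPIRICAL option in the PROC MIXED statement in SAS". On inference it adds: "The p-value will be interpreted at 0.05 level of significance". The tables report standard errors, p-values and two-sided 95% intervals.

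Section 9.5 reuses the same model for liver stiffness (TE) and ELF. Section 15 lists the MMRM among the departures from the protocol, so its specification rests on the SAP. On size, Section 3.3 says that "approximately 50 patients (including at least 20% of patients with CP-C) will be randomized in a 1:1 ratio".

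**The concern.** The sandwich estimator replaces each subject's covariance by the cross-product of that subject's residuals. Fitted residuals are smaller than true errors because each subject has pulled the fit towards itself. With many subjects this does not matter. With about 50, fewer of whom reach Week 48, the variance is understated unless it is corrected.

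The consequence is that confidence intervals in the fallback tend to be too narrow and p-values too low. The MMRM is there to check the ANCOVA, and a check whose standard errors run small can look more convincing than the analysis it is meant to test. Liver biochemistry is a secondary objective (Section 2.1.2), so these tables will be read.

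**Working it through.** **Inputs from the SAP**
- Size (Section 3.3): 20 OCA + 10 placebo + 20 additional = 50, which reproduces the stated total; 25 per arm. The 20 OCA patients come from a simulation whose inputs are not given, so that part cannot be reproduced.
- Dropout (Section 3.3): "assuming a 15% discontinuation rate", stated for the OCA group's PK requirement. It is applied here to both arms: 50 × 0.85 = 42.5 at Week 48.
- Level: 0.05, two-sided (Section 9.3).
- Visits (Section 3): Week 3, Week 6, then about every 6 weeks to Week 48. Read as Weeks 3, 6, 12, 18, 24, 30, 36, 42 and 48, this is 9 visits. The count is inferred; the schedule itself is in the protocol.
- Unstructured covariance parameters: 9 × 10 / 2 = 45.

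**Assumptions not in the SAP**
- True covariance: AR(1) with correlation 0.75, or variance rising over visits with compound-symmetric plus autoregressive correlation.
- Monotone dropout of 15% or 30%; 20% CP-C; one scenario with skewed data.

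**Formulas.** With design X_i, working covariance V_i, residual e_i and A = (Σ X_i′V_i⁻¹X_i)⁻¹, the classical sandwich is A(Σ X_i′V_i⁻¹e_i e_i′V_i⁻¹X_i)A. The Mancl-DeRouen correction replaces e_i by (I − H_i)⁻¹e_i, with H_i = X_i A X_i′V_i⁻¹, which undoes the shrinkage of the residuals.

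**Hand check of the order of magnitude.** If the Week 48 contrast were two plain means with 25 × 0.85 = 21.25 per arm, the SE ratio would be √(1 − 1/21.25) = 0.976. Charging four estimated parameters to 42.5 subjects gives √(1 − 4/42.5) = 0.952. With a normal reference, 2[1 − Φ(1.96 × ratio)] is 5.6% and 6.2%.

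**Simulation at n=50.** There were 4,000 null trials per scenario, with the SAP's fixed effects and the Week 48 treatment difference as target. The working covariance was estimated by moments as an approximation to REML. Monte Carlo error on the type I error is about 0.3 to 0.4 points. The SAP names no df method, so each classical range runs from between-subject df (lower end) to normal reference (upper end). The corrected column uses between-subject df, so it compares with the lower end of the range.

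| True / working structure | Dropout | Classical SE ÷ true | Classical type I | Corrected SE ÷ true | Corrected type I |
|---|---|---|---|---|---|
| AR(1) / AR(1) | 15% | 0.964 | 6.0–6.7% | 1.032 | 4.5% |
| AR(1) / AR(1) | 30% | 0.973 | 5.8–6.4% | 1.051 | 4.2% |
| AR(1) / Toeplitz | 15% | 0.958 | 6.0–6.6% | 1.025 | 4.5% |
| AR(1) / Toeplitz | 30% | 0.920 | 7.9–8.5% | 0.993 | 6.0% |
| Rising variance / AR(1) | 15% | 0.938 | 6.4–7.1% | 1.008 | 4.8% |
| Rising variance / AR(1) | 30% | 0.937 | 6.6–7.5% | 1.015 | 4.9% |
| Rising variance / Toeplitz | 15% | 0.944 | 6.0–6.7% | 1.011 | 4.7% |
| Rising variance / Toeplitz | 30% | 0.945 | 6.4–7.0% | 1.019 | 5.0% |
| Skewed data / AR(1) | 15% | 0.914 | 4.7–5.5% | 0.985 | 3.1% |

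The outer values (8% and 8.5%) come from one cell, AR(1) / Toeplitz with 30% dropout. In that cell even the model-based SE was 0.970 of the truth, so not all of the shortfall there is due to the sandwich.

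**Fewer subjects** (normal data, within-subject or normal df)
- n=40: SE 90% to 96% of true, type I error 6.5% to 8.6%.
- n=30: SE 87% to 94%, type I error 6.7% to 9.8%.
- n=22: SE 84% to 91%, type I error 8.4% to 11.3%.

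**Separate simulation with df held fixed** (2,000 trials per cell, 9 visits, AR(1) working structure). The classical sandwich gave SE 94% to 96% of true and rejection 5.4% to 6.4% at n=50, and 92% and 6.5% to 7.2% at n=40. The correction alone brought the SE to 101% to 104% and rejection to 4.1% to 5.1%.

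**Dropping the sandwich instead.** At n=50 with the true variance rising over visits, model-based SEs were 74% to 75% of true and type I error was about 14% to 15%.

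**The case against.** Several limits on the point stand.

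- **Likelihood of the fallback.** A reader might infer from 45 covariance parameters and about 50 subjects that the unstructured model will probably fail. The documents do not show that. In a small check by Fisher scoring (60 trials per cell, AR(1) data, not PROC MIXED itself), normal data converged 60 times out of 60 in each of three settings: n=50 with 15% dropout, n=50 with 30% dropout plus 5% intermittent missingness, and n=40 with that same missingness. Convergence fell to 65% with skewed, highly correlated data at n=50, and to 65% at n=30. The fallback is possible, not shown to be likely.
- **TE and ELF.** The same shortfall might be read across to Section 9.5. The estimator is the same, but the SAP does not say at how many visits these are measured, so neither the 45-parameter count nor the 9-visit figures carry over.
- **Every dataset.** The bias is an average tendency. With skewed data at n=50 the SE was 91% of true, yet rejection was near nominal.
- **Consequence.** The SAP tests no formal hypothesis (Section 2.2), and this is a fallback inside a sensitivity analysis.
- **Removing EMPIRICAL.** It is tempting to use a structured covariance with Kenward-Roger and no sandwich. Kenward-Roger was not simulated, but it adjusts for small samples given the assumed structure and does not repair a wrong one. The model-based results above speak against this route.

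The objection that better results could come from the df choice alone does not hold: the correction works with df fixed.

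**Conclusion.** The point holds as a modest, conditional one. If the unstructured MMRM fails, the SAP's chosen variance understates the Week 48 standard error by about 3% to 8% on average at n=50. Type I error is then about 5.5% to 8.5% with near-normal data, so a nominal 95% interval covers about 91.5% to 94.5%. With skewed data at n=50 the test is close to nominal. The bias is larger if fewer subjects contribute; Section 13 speaks of limited data but gives no number.

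These sizes rest on the inferred 9 visits, the assumed covariances, AR(1) or Toeplitz working structures and 15% to 30% dropout. The ANCOVA is unaffected and no study conclusion turns on this. It is a cheap improvement, not a flaw in the main analysis.

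**What to change.** Keep a robust estimator in the Section 9.3 fallback, but replace the classical EMPIRICAL sandwich by a small-sample bias-corrected one with subject-level denominator df. A Mancl-DeRouen-type correction will do, for example PROC GLIMMIX with EMPIRICAL=FIRORES or similar. State the df method in the text. Section 9.5 inherits the change by its cross-reference. Do not substitute a model-based Toeplitz or AR(1) covariance without a sandwich.

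The cost is a sentence or two in the SAP before signature, a move from PROC MIXED to another procedure for the fallback, and slightly wider intervals. The corrected test can be somewhat conservative: 3.1% in the skewed scenario at n=50.
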